2.1.4.1 Primary efficacy endpoint

The primary efficacy endpoint is the PCR-corrected ACPR at Day 28. The PCR-corrected ACPR at Day 28 will be derived from the efficacy evaluation at Day 28 defined as follows:

Efficacy evaluation at Day 28	Per Protocol	miITT
	PCR-corrected ACPR at Day 28	PCR-corrected ACPR at Day 28
ACPR	Success	Success
ETF	Failure	Failure
LCF before Day 7	Failure	Failure
LCF on or after Day 7 or LPF		
- P. falciparum recrudescence	Failure	Failure
- P. falciparum reinfection prior to Day 28	Excluded from analysis	Failure
- P. falciparum reinfection on Day 28	Success	Success
- Other species mixed with P. falciparum recrudescence	Failure	Failure
- Other species mixed with P. falciparum reinfection	Excluded from analysis	Failure
- Undetermined, negative or missing PCR	Excluded from analysis	Failure
Rescue therapy start without previous ETF, LCF, LPF, or other species infections, and not classified as a protocol violation	Before Day 7: Failure On/after Day 7: excluded from analysis	Failure
Other species infection without P. falciparum reemergence	Excluded from analysis	Failure
Lost to follow-up	Excluded from analysis	Failure
Withdrawal*	Excluded from analysis	Failure
Protocol violation**	Excluded from analysis	Failure

(*): Patient's request - Investigator's judgement - Adverse event - Other

(**): protocol violations potentially impacting efficacy assessment at Day 28 for the PP population as defined in [Section 2.3.2.2](#)

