10.3.1 Efficacy analyses

All efficacy analyses will be performed on the mITT Population. The efficacy analyses are summarized in Table 8.

Table 8 - Efficacy analyses

Endpoint	Statistical Analysis Methods
 	Otatistical Arialysis methods
For primary objective:Day 28 PCR-corrected ACPR	 The exposure-response association of single-dose OZ439/FQ for PCR-corrected ACPR at Day 28 will demonstrate how the probability of a response in PCR-corrected ACPR at Day 28 increases with exposure (AUC) to OZ439/FQ. Logistic regression with p: probability of PCR-corrected ACPR at Day 28 and OZ439 AUC and FQ AUC_{0-Day28} (SSR97213 AUC_{0-Day28} will be considered also) and baseline parasitemia as covariates will be fitted.
	 Results of logistic regressions of PCR-corrected ACPR on exposure will be provided in a summary table including odds ratio estimates, the corresponding 95% Wald CIs and p-value.
	 Frequency table for Day 28 PCR-corrected ACPR, i.e. proportion, percentage and exact binomial 95% CIs (two-sided by using Clopper-Pearson method for calculating binomial CIs) by treatment arm, will also be provided.
For secondary objectives:	
 Day 28 PCR-corrected ACPR 	 The dose-response exposure-response association of single-dose OZ439/FQ for PCR-corrected ACPR at Day 28 will demonstrate how the probability of a response in PCR-corrected ACPR at Day 28 increases with increasing dose of OZ439/FQ thanks to a logistic regression. Results of logistic regressions of PCR-corrected ACPR on dose will be provided in a summary table including odds ratio estimates, the corresponding 95% Wald Cls, and p-value.
 Parasitemia at baseline then every 6 h during the first 36 h then at 48 h and every 24 h until Day 7 	 Descriptive statistics (number of observations [n], mean, geometric mean, standard deviation [SD], median, first quartile [Q1], third quartile [Q3], minimum, and maximum) for parasitemia data (number of parasites/µL) (raw data and absolute change from baseline) will be displayed at each post-baseline assessment. Time profile plots (Mean ± standard error of the mean) of parasitemia will be provided for each treatment arm, one curve per arm.
Day 28 crude ACPR	 Same analysis using Clopper-Pearson method as for PCR-corrected ACPR will be done on crude ACPR at Day 28. The exposure-response (respectively dose- response) association of single-dose OZ439/FQ for crude ACPR will also be evaluated.

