10.3.1.1 Definition of ACPR, recrudescence, and re-infection

ACPR is defined based on WHO recommendations (2) as follows:

ACPR

• absence of parasitemia (blood films) on Day 28, irrespective of axillary temperature, without previously meeting any of the criteria of early treatment failure or late clinical failure or late parasitological failure (see definitions in Section 7.7.1) or having received a rescue treatment for malaria in the conditions defined in Section 7.7.1.

Recrudescence

• appearance of asexual parasites after clearance of initial infection with a genotype identical to that of parasites present at baseline.

Re-infection

• appearance of asexual parasites after clearance of initial infection with a genotype that differs from that of parasites present at baseline. Confirmed new infection will not be regarded as treatment failure or recrudescence.

Crude ACPR

• Crude ACPR applies to both recrudescence of the parasite clone responsible for baseline infection and re-infection by a different clone.

PCR-corrected ACPR

• the PCR-corrected ACPR applies only to recrudescence (re-emergence of the original clone of parasite that is present at baseline). Recrudescence is distinguished from reinfection by genotyping the parasite clone.

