1.5 MODIFICATIONS TO THE STATISTICAL SECTION OF THE PROTOCOL

The statistical section of the protocol was never changed in an amendment.
There are no planned interim analyses.

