1.6 STATISTICAL MODIFICATIONS MADE IN THE STATISTICAL ANALYSIS PLAN

The primary efficacy population will be the PK/PD population instead of the mITT population stated in the protocol.

A per-protocol [PP] population was added in order to align the analysis population with the primary endpoint of the study. All populations have been further clarified from the protocol definitions

The derivation of the secondary endpoint, Fever clearance time (FCT), has been added. FCT will be assessed by measuring the time from the first dose until the first time that the body temperature dropped and remained <37.5 °C.

Time to 50% parasite reduction (T_{PC50}) will also be calculated in addition to the time to 99% PR.

The evaluation of the relationship between parasitemia (as measured on thick blood film and/or by qPCR) and concentration of OZ439/FQ may be performed in a separate analysis pooling data from different studies and be reported in a separate report.

The terminal half-life ($t_{1/2}$) for OZ439 and ferroquine will not be estimated as this endpoint does not contribute to the objectives of the study.

The definition of baseline to be used for efficacy analyses has been clarified.

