Recrudescence: The appearance of asexual parasites after clearance of initial infection with a genotype identical to that of parasites present at baseline. Recrudescence is confirmed by microscopy (positive blood smear) and by genotyping PCR analysis.

Re-infection: The appearance of asexual parasites after clearance of initial infection with a genotype that differs from that of parasites present at baseline. Re-infection is confirmed by microscopy (positive blood smear) and by genotyping PCR analysis.

Treatment failure: Any patients who met any of the criteria for ETF, LCF or LPF.

Crude ACPR does not distinguish between re-infection (by a new clone of parasite) and recrudescence (re-emergence of the original clone of parasite that was present at baseline); i.e. presence of either a new clone or genotypically identical parasite will be considered a treatment failure.

PCR-corrected ACPR applies only to recrudescence; (i.e. patients with re-infection are considered non-evaluable for the analysis of PCR-adjusted ACPR). Presence of a genotypically identical parasite will be considered a treatment failure.

Genotyping adjustment

LCF occurring from Day 7 or LPF will be sub-classified as follows using parasite genotyping results:

- *P. falciparum* recrudescence, if no other species reported in eCRF and genotyping result is “recrudescence”
- *P. falciparum* reinfection, if no other species reported in eCRF and genotyping result is “reinfection”

- Other species with *P. falciparum* recrudescence, if other species reported in eCRF and genotyping result is “recrudescence”
- Other species with *P. falciparum* reinfection, if other species reported in eCRF and genotyping result is “reinfection”
- Undetermined, negative or missing PCR, if genotyping result is “Undetermined”, “negative”, “undetermined” or “missing”, with or without other species infection.

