2.1.4.2 Secondary efficacy endpoints

2.1.4.2.1 Crude ACPR at Day 28

Derived from the efficacy evaluation at Day 28 defined as follows:

Efficacy evaluation at Day 28	Per-Protocol Crude ACPR at Day 28	miITT Crude ACPR at Day 28
ACPR	Success	Success
ETF	Failure	Failure
LCF before Day 7	Failure	Failure
LCF on or after Day 7 or LPF		
- P. falciparum recrudescence	Failure	Failure
- P. falciparum reinfection prior to Day 28	Failure	Failure
- P. falciparum reinfection on Day 28	Failure	Failure
- Other species mixed with P. falciparum recrudescence	Failure	Failure
- Other species mixed with P. falciparum reinfection	Failure	Failure
- Undetermined, negative or missing PCR	Failure	Failure
Other species infection without P. falciparum reemergence	Excluded from analysis	Failure
Rescue therapy start without previous ETF, LCF, LPF, or other species infections, and not classified as a protocol violation	Failure	Failure
Lost to follow-up	Excluded from analysis	Failure
Withdrawal*	Excluded from analysis	Failure
Protocol violation**	Excluded from analysis	Failure

(*): Patient's request - Investigator's judgement - Adverse event - Other

(**): protocol violations potentially impacting efficacy assessment at Day 28 for the PP population are defined in [Section 2.3.2.2](#)

2.1.4.2.2 Parasitemia at baseline then every 6 h during the first 36 h then at 48 h and every 24 h until Day 7

Parasitemia is the quantitative content of parasites in the blood. It is used as a measurement of parasite load in the organism and an indication of the degree of an active parasitic infection.

The methods to be used for quantifying parasitemia depend on the parasitic species and its life cycle. The number of plasmodia can be counted using an optical microscope, on a special thick film (for low parasitemias) or thin film blood smear (for high parasitemias).

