2.4.4 Analyses of efficacy endpoints

The primary analysis detailed in [Section 2.4.4.1.1](#) will be carried out on the PK/PD efficacy population.

All statistical analyses on secondary efficacy endpoints as well as on [Section 2.4.4.1.2](#) and [Section 2.4.4.1.3](#) will be performed on the mITT population only, unless otherwise stated.

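### The mITT column for PCR-corrected ACPR counts re-infection before Day 28 as failure, against the protocol's definition, and the SAP does not declare the change

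*SAP*

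**What the plan says.** **Protocol.** Section 10.3.1.1 restricts PCR-corrected ACPR to recrudescence and states: "Confirmed new infection will not be regarded as treatment failure or recrudescence". Section 10.3.1 adds: "All efficacy analyses will be performed on the mITT Population". The definition was therefore written with mITT as the analysis set.

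**SAP, text.** Section 2.1.4 says that "patients with re-infection are considered non-evaluable for the analysis of PCR-adjusted ACPR", without limiting this to one population. Section 2.3.2.2 repeats the rule inside the per-protocol (PP) definition and refers back to 2.1.4.

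**SAP, table.** In 2.1.4.1 the row for "reinfection prior to Day 28" and the row for another species mixed with P. falciparum re-infection are excluded in the PP column and Failure in the mITT column. Re-infection found on Day 28 is Success in both. There is no column for the PK/PD efficacy population.

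**SAP, declared changes.** Section 1.5 says: "The statistical section of the protocol was never changed in an amendment". Section 1.6 declares, among other things: "The primary efficacy population will be the PK/PD population instead of the mITT population stated in the protocol". It also adds the PP population and says that populations were clarified. It says nothing about the coding of re-infection.

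**SAP, where the column is used.** Section 2.4.4 says that the descriptive analysis (2.4.4.1.2) and the dose-response (2.4.4.1.3) of PCR-corrected ACPR "will be performed on the mITT population only, unless otherwise stated". Section 2.4.4.1.2 then asks for the frequency table in both PP and mITT. The summary of statistical analyses at the end of the SAP lists PP for the dose-response.

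**The concern.** PCR correction exists to separate drug failure from a new infection. A column that scores confirmed new infections as failures removes that separation but keeps the endpoint's name. If re-infection is unrelated to OZ439, the recoding adds failures to every arm, and adds most where success is highest. That pulls the OZ439 odds ratio towards 1.

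The dose-response of PCR-corrected ACPR belongs to the first secondary objective. The text and the table of the SAP support different codings, and the trial is open label. If this stays unresolved, the coding could be chosen after the genotyping results are known.

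**Working it through.** **1. Row comparison of the two mITT columns (SAP 2.1.4.1 and 2.1.4.2.1).** For crude ACPR, every mITT row except ACPR is Failure. For PCR-corrected ACPR, every mITT row except ACPR and Day 28 re-infection is Failure. The only row that differs is "reinfection on Day 28": Failure for crude, Success for PCR-corrected.

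**2. The plan's own figures.** Protocol 10.1 and Appendix 8 give about 90% power with 30 evaluable per arm, for the exposure-response Wald test. A simulation of equation 2 used the stated coefficients and parasitemia distribution, with concentrations calibrated to the stated arm rates. It assumed an FQ CV of 40% and a correlation of 0.2, because the documents give neither. Power was 91.6%, 91.3% and 87.6% at assumed OZ439 CVs of 50%, 80% and 120%. Enrolment also agrees: 30/0.85 = 35.3 per arm.

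**3. Inputs for the effect of the coding.** Arm success p = 72/81/91/97% at 0/300/600/1000 mg and a two-sided 5% Wald test (Appendix 8), with 30 per arm. The re-infection proportion r among patients who would otherwise succeed is assumed, equal in all arms.

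**4. Formulas.** Coded Failure, success is p(1−r). Coded excluded, the odds are p(1−r)/(1−p), so (1−r) cancels from the odds ratio.

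**5. Odds ratio, 1000 versus 0 mg, no other failure row.**
- r = 0: (0.97/0.03)/(0.72/0.28) = 32.33/2.571 = 12.6.
- r = 5%, Failure: (0.9215/0.0785)/(0.684/0.316) = 11.74/2.165 = 5.4.
- r = 5%, excluded: 12.6.
- Risk difference at 5%, Failure: 25.0 × 0.95 = 23.8 points.

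**6. The same with an assumed 10% failing through the other mITT rows** (loss to follow-up, withdrawal, protocol violation, undetermined PCR and so on). Success becomes 0.9p.
- r = 0, or re-infections excluded: (0.873/0.127)/(0.648/0.352) = 6.874/1.841 = 3.7.
- r = 5%, Failure: (0.8294/0.1706)/(0.6156/0.3844) = 4.860/1.601 = 3.0.

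**7. Power of an unadjusted linear-dose Wald test** (simulation, 10,000 to 20,000 trials per setting):

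| Other rows | r | Odds ratio, Failure | Power, Failure | Power, excluded |
|---|---|---|---|---|
| none | 0% | 12.6 | about 0.87 | about 0.87 |
| none | 2% | 8.0 | 0.81 | 0.86 |
| none | 5% | 5.4 | 0.71 | 0.86 |
| none | 10% | 3.7 | 0.59 | 0.85 |
| 10% | 2% | 3.4 | 0.56 | 0.59 |
| 10% | 5% | 3.0 | 0.50 | 0.58 |

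A rerun agreed to within about 0.015. A separate dose model adjusted for baseline parasitemia gave the same direction: 74% with no re-infection and, at 5%, 63% (Failure) against 73% (excluded).

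**8. Patients removed by exclusion at 5%:** 30 × (0.72 + 0.81 + 0.91 + 0.97) × 0.05 = 5.1 of 120.

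**The case against.** The strongest defence is that the mITT column is a deliberate conservative analysis. Every outcome that PP excludes is Failure in mITT: re-infection before Day 28, mixed re-infection, undetermined PCR, rescue on or after Day 7, other species, loss to follow-up, withdrawal and protocol violation. SAP 2.3.2.2 and 2.4.4.1.2 discuss non-evaluability in a PP context, and SAP 1.6 says that PP was added to match the primary endpoint. This reading is plausible. But the SAP nowhere labels the column that way, 2.1.4 states its rule generally, and the protocol's definition says the opposite.

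A reader might infer that scoring Day 28 re-infection as Success disproves such a rule. It does not: PP also scores that row Success, so the table does not treat it as non-evaluable. The row does conflict with 2.1.4, but that is a separate point.

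A reader might also infer that mITT has no recrudescence-only result. It has one. SAP 2.1.4.2.5 censors time to recrudescence at a re-infection on or after Day 7, 2.4.4.2 places that endpoint on mITT, and 2.4.4.2.8 gives Kaplan-Meier estimates by arm. The PP frequency table also leaves out re-infections before Day 28.

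On size, the fall from 12.6 to 5.4 needs every other failure row to be empty. Protocol 10.1 anticipates around 15% early dropout, and some of those patients may still be in mITT. Protocol 5.4 aims for a low re-infection risk.

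**Conclusion.** The conflict stands on the text alone and should be fixed. The mITT coding of both re-infection rows contradicts protocol 10.3.1.1 and SAP 2.1.4, and SAP 1.6 does not declare it.

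Its reach is limited to the mITT frequency table and to the PCR-corrected dose-response, if that analysis is run on mITT. The documents do not support the stronger reading that the primary result is biased. The PK/PD efficacy population has no column in 2.1.4.1, and its exclusion list (2.3.5.1) does not name re-infection. But that list takes over exclusions from the PP column, 2.1.4 is general, and the SAP's closing summary lists PP, so exclusion is the likely intent.

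The direction of the bias rests on re-infection being independent of OZ439. Its size depends on a rate the documents do not give and on how often the other failure rows occur. At 5% re-infection the power loss is about 15 points with those rows empty and about 8 points with 10% in them. The risk difference moves little, and excluding re-infections would not return mITT to 12.6 if other failure rows occur.

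**What to change.** Before database lock:

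- In SAP 2.1.4.1, code both re-infection rows as excluded (non-evaluable) for PCR-corrected ACPR in the main mITT analysis. Keep Failure for crude ACPR.
- If the Failure version is wanted, keep it only as a named sensitivity analysis and declare it in SAP 1.6.
- State the same re-infection coding for the PK/PD efficacy population, preferably as a third column.
- Reconcile the Day 28 re-infection row (Success) with the non-evaluable rule in 2.1.4.
- Reconcile the population for the PCR-corrected dose-response between SAP 2.4.4 (mITT) and the closing summary (PP).

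This takes table and text edits and no new data. The cost is a small exclusion from mITT on a post-randomisation event, about 5 of 120 patients at 5% re-infection. Undetermined PCR would stay Failure, so the scoring of a new infection would depend on whether genotyping succeeds. The declared sensitivity analysis would show how much that matters.

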2.3.2 Efficacy populations

2.3.2.1 *Modified Intent-to-treat population*

The modified intent-to-treat (mITT) population includes all randomized patients who received the single administration of IMP, with parasitologically confirmed *P. falciparum* malaria at baseline, having parasitemia data post-randomization.

For analyses and displays, patients will be classified according to the randomized treatment regardless of actual treatment received.

2.3.2.2 *Per-protocol population*

The per-protocol (PP) is the population receiving at least the single administration of FQ 400mg/OZ439, with parasitologically confirmed malaria at baseline, having parasitemia data post-randomization in order to be evaluable for Day 28 ACPR, without major protocol violations possibly affecting efficacy outcome. Note PCR-corrected ACPR applies only to recrudescence i.e. patients with new infections are considered non-evaluable for the analysis of PCR-corrected ACPR see Section 2.1.4).

Parasitemia data for patients with rescue treatment started before the considered time point will be excluded from this time point until Day 28.

In case of vomiting or other reasons interrupting the administration of the complete dose, and if valid parasitemia data post-randomization available, then patients will be included in the PP population.

As defined in [Section 2.1.4.1](#), there are certain criteria that would exclude patients from having an evaluable PCR-corrected ACPR at Day 28:

- Other species infection without *P. falciparum* reemergence,
- Lost to follow-up,
- Withdrawal,
- Protocol violation.

Protocol violations considered above are those potentially impacting efficacy assessments at Day 28:

- Patients who did not take IMP or who needed rescue treatment due to vomiting during IMP administration. Start of vomiting will be classified in 3 categories (< 5 minutes, [5-35] minutes, > 35 minutes and < 6 hours).
- Patient presenting severe malaria or receiving a rescue treatment due to severe malaria during the first 24 hours following IMP start (i.e. wrong inclusion).
- Start of rescue therapy before Day 28 assessment not due to: vomiting during IMP administration, wrong inclusion, treatment failure (per investigator or per WHO criteria), or other species infections.
- Missing baseline parasitemia, and positive parasitemia at 48 or 72 hours.
- Intermittent missing or out of window post-baseline parasitemia preventing to evaluate ACPR Day 28.

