- Missing post-baseline body temperature preventing to evaluate ACPR Day 28.
- Out of Day 28 time window parasitemia preventing to evaluate ACPR Day 28.
- Patients who received treatment that differs from the randomized one.
- Patients re-dosed while they should not according to the protocol.
- Patients not re-dosed while they should have been according to the protocol.
- Patients with at least one enrolment violation among the following:
 - Patients who meet exclusion criteria E 01 which is: “Presence of severe malaria (according to WHO definition)”.
 - Patients violator for inclusion criteria I02 which is: “Presence of *P. falciparum* malaria, with a fever as defined with axillary temperature ≥ 37.5 degree Celsius ($^{\circ}\text{C}$) or oral/rectal/ tympanic temperature $\geq 38^{\circ}\text{C}$ or history of fever in the previous 24 hours (history of fever must be documented), with a mono-infection with *P. falciparum* and parasitemia (microscopically, blood smear) $\geq 3,000$ and $\leq 50,000$ asexual parasites/ μL of blood Microscopically (blood smear) confirmed parasite infection, ranging from 3000 to 50000 asexual parasites/ μL of blood”.
 - Patients violator for exclusion criteria E07 who would be treated with anti-malarial treatment:
 - from 6 weeks (with PQP-based compound, mefloquine, naphthoquine or sulphadoxine/pyrimethamine) before IMP administration,
 - 4 weeks (with amodiaquine or chloroquine) before IMP administration,
 - 14 days (quinine, halofantrine, lumefantrine-based compounds and any other anti-malarial treatment or antibiotics with antimalarial activity) before IMP administration,
 - 7 days (herbal products or traditional medicines) before IMP administration.

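### In the mITT outcome tables, patients with entry or dosing deviations can be scored Failure although their Day 28 cure was observed

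*SAP*

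**What the plan says.** The protocol-violation row of the PCR-corrected ACPR table in SAP 2.1.4.1 reads "Protocol violation Excluded from analysis Failure", the PP column first and the mITT column second. The footnote defines the row by reference: "protocol violations potentially impacting efficacy assessment at Day 28 for the PP population as defined in" SAP 2.3.2.2. The crude ACPR table in 2.1.4.2.1 has the same row and an equivalent footnote: "protocol violations potentially impacting efficacy assessment at Day 28 for the PP population are defined in" the same section.

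The 2.3.2.2 list mixes two kinds of item.

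- **Outcome missing or overtaken by rescue:** missing or out-of-window films or temperatures that prevent evaluation of ACPR, and rescue after vomiting or for early severe malaria.
- **Outcome can be fully observed:** "Patients who received treatment that differs from the randomized one"; re-dosing that should not have happened; "Patients not re-dosed while they should have been according to the protocol"; and violations of I02 (fever, mono-infection, 3,000 to 50,000 parasites/µL) or E07 (recent antimalarials or herbal products).

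The mITT population (2.3.2.1) "includes all randomized patients who received the single administration of IMP" and who have confirmed *P. falciparum* at baseline and later parasitemia data. It classifies them by randomized arm whatever they actually received. SAP 2.4.4 says that the secondary efficacy analyses, and the descriptive and dose-response analyses of PCR-corrected ACPR, "will be performed on the mITT population only, unless otherwise stated".

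**The concern.** ACPR in SAP 2.1.4 Table 1 and protocol 10.3.1.1 depends on parasitemia, the WHO failure criteria and rescue. SAP 2.1.4 defines treatment failure as ETF, LCF or LPF. Neither definition mentions eligibility or dosing deviations. A patient in the second group above can clear, stay parasite-free to Day 28 without rescue, and so meet the definition of success, yet also fall in the row that mITT scores as Failure.

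This is not conservative handling of missing data, because the outcome is known. It also conflicts with the as-randomized rule of mITT: receiving another treatment does not change the arm but would change the outcome.

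At stake is the first secondary objective, the dose-response of OZ439 on PCR-corrected and crude ACPR, together with the mITT response rates by arm. The planned cure rate at 1000 mg is 97%, so the high-dose arm has very few true failures and a handful of artificial ones weighs heavily on the odds scale.

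**Working it through.** **1. Which row wins?** The tables give no order. SAP 2.3.2.2 says, with reference to 2.1.4.1, that a protocol violation is among the criteria that exclude a patient from having an evaluable PCR-corrected ACPR. In the PP column the violation row therefore overrides ACPR = Success. Read the same way, the mITT column turns the cure into a Failure. This is an inference, not a stated rule.

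**2. Is the primary test affected?** It uses the PK/PD efficacy population (2.3.5.1, 2.4.4), where listed violations are not evaluable rather than failures. That section's list omits the wrong-treatment and re-dosing items. A cured patient with such a deviation could thus be a Success in the primary analysis and a Failure in mITT.

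**3. Inputs.** ACPR rates of 72/81/91/97% at OZ439 0/300/600/1000 mg, 30 evaluable and 35 randomized per arm, two-sided 5% Wald test (protocol 10.1 and Appendix 8; SAP 1.3 and 2.4.4.2.1.1). The share *v* of cured patients carrying a listed deviation is not in the documents and is an assumption.

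**4. Reproducing the plan's figure.** The plan states power of around 90% for the exposure test at 30 per arm. Simulating eq 2 with the stated coefficients and truncated parasitemia, with concentrations calibrated to the four rates, gives 90 to 93%. The concentration spread is not in the documents; four sets were tried (FQ CV 30-50%, OZ439 CV 50-100%, correlation 0.2). No power is stated for the dose-trend test. Simulated on dose alone, without covariates, it is about 87% at 30 per arm and 91% at 35.

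**5. Effect of recoding, equal *v* in all arms.** Recoded rate = p(1 − v). Cures recoded at 30 per arm = 30 × (0.72 + 0.81 + 0.91 + 0.97) × v = 102.3v.

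| v | Cures recoded (30/arm) | Rates A/B/C/D (%) | Odds ratio D vs A | Power, 30/arm | Power, 35/arm |
|---|---|---|---|---|---|
| 0 | 0 | 72/81/91/97 | 12.6 | 87% | 91% |
| 1% | 1.0 | 71.3/80.2/90.1/96.0 | 9.7 | 84% | 89% |
| 2% | 2.0 | 70.6/79.4/89.2/95.1 | 8.0 | 80% | 86% |
| 5% | 5.1 | 68.4/77.0/86.5/92.2 | 5.4 | 72% | 78% |
| 10% | 10.2 | 64.8/72.9/81.9/87.3 | 3.7 | 60% | 67% |

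Power figures are simulated; repeat runs of 5,000 to 20,000 trials agree to about one point.

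Why so few patients matter: at v = 5% and 30 per arm, arm D goes from 30 × 0.03 = 0.9 expected failures to 0.9 + 30 × 0.97 × 0.05 = 2.4. Arm A goes from 8.4 to 8.4 + 30 × 0.72 × 0.05 = 9.5. The D − A difference barely moves (25.0 to 23.8 points), but the odds ratio more than halves.

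**6. Unequal *v*, 30 per arm.** With deviations only in arms B-D, power is about 60% at v = 5%. With deviations only in arm A, it rises to about 92% at 5% and 96% at 10%, an exaggerated trend.

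**The case against.** The strongest reply is that precedence is not stated, and the row could be meant only for patients who fit no other row. The PP definition already removes violators whatever the table order. SAP 2.1.4 sends to this list cases whose ACPR cannot be evaluated, and the rescue row is limited to cases not classed as a "protocol violation". So a reader who infers that the SAP states outright that every listed violator is a Failure goes too far. What stands is that the footnote invokes the whole list without that limit, and two programmers could score the same cured patient oppositely.

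Other stronger inferences also fail.

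- **That the primary analysis is biased.** It does not use the mITT column.
- **That the recoding always dilutes the dose-response.** The direction depends on where the deviations fall.
- **That both re-dosing items are confined to arms B-D.** SAP 2.3.3 provides for erroneous FQ re-dosing, which can happen in arm A. Only the omitted OZ439 re-dose (protocol 7.1.1.2) is confined to B-D.
- **That rates of 5% or more are to be expected.** Nothing in the documents supports this. Waivers are prohibited, dosing is supervised and kits are reconciled, so 1 to 2% may be nearer.

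The base is uncertain too. If all 35 per arm enter mITT and about 14% are lost and scored Failure, dose-trend power is already about 58%, and a further 5% recoding takes it to about 49%.

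Finally, Failure for violators is a known conservative convention, and an E07 violator's cure may owe something to the earlier drug. That supports a sensitivity analysis; it does not support overriding observed outcomes in the main mITT result.

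**Conclusion.** The concern holds for the secondary mITT analyses. On its natural reading, the violation row lets an observed Day 28 cure be scored Failure, contrary to the SAP's definitions of ACPR and treatment failure and to the mITT as-randomized rule. On the narrower reading the wording is still incomplete.

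The size depends on an unknown rate. One or two recoded cures at 30 per arm cost about 3 to 7 points of dose-trend power; five cost about 15. These figures assume the planned rates, deviations spread equally over arms, no other losses and no covariates in the model. A concentration in B-D weakens the trend further and one in arm A inflates it.

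The population itself is also unsettled: SAP 2.4.4 names mITT for the dose-response regressions, while the summary of statistical analyses in Appendix B names PP. The planned PP frequency table (2.4.4.1.2) gives a comparison but does not correct the mITT result.

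**What to change.** - In the mITT columns of 2.1.4.1 and 2.1.4.2.1, classify patients with entry, wrong-treatment or re-dosing deviations by their observed outcome, using the other rows.
- Keep Failure for listed deviations that leave Day 28 ACPR unevaluable or that involve rescue.
- State the row precedence for each column. Leave the PP column unchanged.
- Keep failure-for-all violators as a sensitivity analysis, and report the number recoded by arm.
- Reconcile SAP 2.4.4 with the Appendix B summary on mITT versus PP for the dose-response analyses.

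The cost is wording in two tables and a programming change before database lock, with no new data. The downside is that some cures confounded by earlier antimalarial use (E07) count as mITT successes; the PP and sensitivity analyses cover that.
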